### **8.2.2. Pregnancy Testing**

Pregnancy tests may be urine or serum tests, but must have a sensitivity of at least 25 mIU/mL. Pregnancy tests will be performed in WOCBP at the times listed in the [SoA](#). Following a negative pregnancy test result at screening, appropriate contraception must be commenced and a second negative pregnancy test result will be required at the baseline visit prior the participant's receiving the study intervention. Pregnancy tests will also be done whenever 1 menstrual cycle is missed during the active treatment period (or when potential pregnancy is otherwise suspected) and at the end of the study. Pregnancy tests may also be repeated if requested by IRBs/ ECs or if required by local regulations. If a urine test cannot be confirmed as negative (eg, an ambiguous result), a serum pregnancy test is required. In such cases, the participant must be excluded if the serum pregnancy result is positive.

## **8.3. Adverse Events and Serious Adverse Events**

The definitions of an AE and an SAE can be found in [Appendix 3](#).

AEs will be reported by the participant (or, when appropriate, by a caregiver, surrogate, or the participant's legally authorized representative).

The investigator and any qualified designees are responsible for detecting, documenting, and recording events that meet the definition of an AE or SAE and remain responsible to pursue and obtain adequate information both to determine the outcome and to assess whether the

event meets the criteria for classification as an SAE or caused the participant to discontinue the study intervention (see [Section 7.1](#)).

Each participant/parent/legal guardian will be questioned about the occurrence of AEs in a nonleading manner.

In addition, the investigator may be requested by Pfizer Safety to obtain specific follow-up information in an expedited fashion.

### **8.3.1. Time Period and Frequency for Collecting AE and SAE Information**

The time period for actively eliciting and collecting AEs and SAEs (“active collection period”) for each participant begins from the time the participant provides informed consent, which is obtained before the participant’s participation in the study (ie, before undergoing any study-related procedure and/or receiving study intervention), through and including a minimum of 28 calendar days, except as indicated below, after the last administration of the study intervention.

Follow-up by the investigator continues throughout and after the active collection period and until the AE or SAE or its sequelae resolve or stabilize at a level acceptable to the investigator and Pfizer concurs with that assessment.

For participants who are screen failures, the active collection period ends when screen failure status is determined.

If the participant withdraws from the study and also withdraws consent for the collection of future information, the active collection period ends when consent is withdrawn.

If a participant definitively discontinues or temporarily discontinues study intervention because of an AE or SAE, the AE or SAE must be recorded on the CRF and the SAE reported using the CT SAE Report Form.

Investigators are not obligated to actively seek AEs or SAEs after the participant has concluded study participation. However, if the investigator learns of any SAE, including a death, at any time after a participant has completed the study, and he/she considers the event to be reasonably related to the study intervention, the investigator must promptly report the SAE to Pfizer using the CT SAE Report Form.

#### **8.3.1.1. Reporting SAEs to Pfizer Safety**

All SAEs occurring in a participant during the active collection period as described in Section 8.3.1 are reported to Pfizer Safety on the CT SAE Report Form immediately upon awareness and under no circumstance should this exceed 24 hours, as indicated in [Appendix 3](#). The investigator will submit any updated SAE data to the sponsor within 24 hours of it being available.

### **8.3.1.2. Recording Nonserious AEs and SAEs on the CRF**

All nonserious AEs and SAEs occurring in a participant during the active collection period, which begins after obtaining informed consent as described in Section 8.3.1, will be recorded on the AE section of the CRF.

The investigator is to record on the CRF all directly observed and all spontaneously reported AEs and SAEs reported by the participant.

### **8.3.2. Method of Detecting AEs and SAEs**

The method of recording, evaluating, and assessing causality of AEs and SAEs and the procedures for completing and transmitting SAE reports are provided in [Appendix 3](#).

Care will be taken not to introduce bias when detecting AEs and/or SAEs. Open-ended and nonleading verbal questioning of the participant is the preferred method to inquire about AE occurrences.

### **8.3.3. Follow-up of AEs and SAEs**

After the initial AE/SAE report, the investigator is required to proactively follow each participant at subsequent visits/contacts. For each event, the investigator must pursue and obtain adequate information until resolution, stabilization, the event is otherwise explained, or the participant is lost to follow-up (as defined in [Section 7.3](#)).

In general, follow-up information will include a description of the event in sufficient detail to allow for a complete medical assessment of the case and independent determination of possible causality. Any information relevant to the event, such as concomitant medications and illnesses, must be provided. In the case of a participant death, a summary of available autopsy findings must be submitted as soon as possible to Pfizer Safety.

Further information on follow-up procedures is given in [Appendix 3](#).

### **8.3.4. Regulatory Reporting Requirements for SAEs**

Prompt notification by the investigator to the sponsor of an SAE is essential so that legal obligations and ethical responsibilities towards the safety of participants and the safety of a study intervention under clinical investigation are met.

The sponsor has a legal responsibility to notify both the local regulatory authority and other regulatory agencies about the safety of a study intervention under clinical investigation. The sponsor will comply with country-specific regulatory requirements relating to safety reporting to the regulatory authority, IRBs/ECs, and investigators.

Investigator safety reports must be prepared for SUSARs according to local regulatory requirements and sponsor policy and forwarded to investigators as necessary.

An investigator who receives SUSARs or other specific safety information (eg, summary or listing of SAEs) from the sponsor will review and then file it along with the SRSD(s) for the study and will notify the IRB/EC, if appropriate according to local requirements.

### **8.3.5. Exposure During Pregnancy or Breastfeeding, and Occupational Exposure**

Exposure to the study intervention under study during pregnancy or breastfeeding and occupational exposure are reportable to Pfizer Safety within 24 hours of investigator awareness.

#### **8.3.5.1. Exposure During Pregnancy**

An EDP occurs if:

- A female participant is found to be pregnant while receiving or after discontinuing study intervention.
- A male participant who is receiving or has discontinued study intervention exposes a female partner prior to or around the time of conception.
- A female is found to be pregnant while being exposed or having been exposed to study intervention due to environmental exposure. Below are examples of environmental exposure during pregnancy:
  - A female family member or healthcare provider reports that she is pregnant after having been exposed to the study intervention by ingestion, inhalation or skin contact.
  - A male family member or healthcare provider who has been exposed to the study intervention by ingestion, inhalation or skin contact then exposes his female partner prior to or around the time of conception.

The investigator must report EDP to Pfizer Safety within 24 hours of the investigator's awareness, irrespective of whether an SAE has occurred. The initial information submitted should include the anticipated date of delivery (see below for information related to termination of pregnancy).

- If EDP occurs in a participant or a participant's partner, the investigator must report this information to Pfizer Safety on the CT SAE Report Form and an EDP Supplemental Form, regardless of whether an SAE has occurred. Details of the pregnancy will be collected after the start of study intervention and until at least 5 terminal half-lives after the last dose.
- If EDP occurs in the setting of environmental exposure, the investigator must report information to Pfizer Safety using the CT SAE Report Form and EDP Supplemental Form. Since the exposure information does not pertain to the participant enrolled in

the study, the information is not recorded on a CRF; however, a copy of the completed CT SAE Report Form is maintained in the investigator site file.

Follow-up is conducted to obtain general information on the pregnancy and its outcome for all EDP reports with an unknown outcome. The investigator will follow the pregnancy until completion (or until pregnancy termination) and notify Pfizer Safety of the outcome as a follow-up to the initial EDP Supplemental Form. In the case of a live birth, the structural integrity of the neonate can be assessed at the time of birth. In the event of a termination, the reason(s) for termination should be specified and, if clinically possible, the structural integrity of the terminated fetus should be assessed by gross visual inspection (unless preprocedure test findings are conclusive for a congenital anomaly and the findings are reported).

Abnormal pregnancy outcomes are considered SAEs. If the outcome of the pregnancy meets the criteria for an SAE (ie, ectopic pregnancy, spontaneous abortion, intrauterine fetal demise, neonatal death, or congenital anomaly in a live-born baby, a terminated fetus, an intrauterine fetal demise, or a neonatal death), the investigator should follow the procedures for reporting SAEs. Additional information about pregnancy outcomes that are reported to Pfizer Safety as SAEs follows:

- Spontaneous abortion including miscarriage and missed abortion;
- Neonatal deaths that occur within 1 month of birth should be reported, without regard to causality, as SAEs. In addition, infant deaths after 1 month should be reported as SAEs when the investigator assesses the infant death as related or possibly related to exposure to the study intervention.

Additional information regarding the EDP may be requested by the sponsor. Further follow-up of birth outcomes will be handled on a case-by-case basis (eg, follow-up on preterm infants to identify developmental delays). In the case of paternal exposure, the investigator will provide the participant with the Pregnant Partner Release of Information Form to deliver to his partner. The investigator must document in the source documents that the participant was given the Pregnant Partner Release of Information Form to provide to his partner.

### **8.3.5.2. Exposure During Breastfeeding**

An exposure during breastfeeding occurs if:

- A female participant is found to be breastfeeding while receiving or after discontinuing study intervention.
- A female is found to be breastfeeding while being exposed or having been exposed to study intervention (ie, environmental exposure). An example of environmental exposure during breastfeeding is a female family member or healthcare provider who

reports that she is breastfeeding after having been exposed to the study intervention by inhalation or skin contact.

The investigator must report exposure during breastfeeding to Pfizer Safety within 24 hours of the investigator's awareness, irrespective of whether an SAE has occurred. The information must be reported using the CT SAE Report Form. When exposure during breastfeeding occurs in the setting of environmental exposure, the exposure information does not pertain to the participant enrolled in the study, so the information is not recorded on a CRF. However, a copy of the completed CT SAE Report Form is maintained in the investigator site file.

An exposure during breastfeeding report is not created when a Pfizer drug specifically approved for use in breastfeeding women (eg, vitamins) is administered in accord with authorized use. However, if the infant experiences an SAE associated with such a drug, the SAE is reported together with the exposure during breastfeeding.

#### **8.3.5.3. Occupational Exposure**

An occupational exposure occurs when a person receives unplanned direct contact with the study intervention, which may or may not lead to the occurrence of an AE. Such persons may include healthcare providers, family members, and other roles that are involved in the trial participant's care.

The investigator must report occupational exposure to Pfizer Safety within 24 hours of the investigator's awareness, regardless of whether there is an associated SAE. The information must be reported using the CT SAE Report Form. Since the information does not pertain to a participant enrolled in the study, the information is not recorded on a CRF; however, a copy of the completed CT SAE Report Form is maintained in the investigator site file.

#### **8.3.6. Cardiovascular and Death Events**

Not applicable

#### **8.3.7. Disease Related Events and/or Disease Related Outcomes Not Qualifying as AEs or SAEs**

Not applicable

#### **8.3.8. Adverse Events of Special Interest**

Not applicable

##### **8.3.8.1. Lack of Efficacy**

Lack of efficacy is reportable to Pfizer Safety only if associated with an SAE.

#### **8.3.9. Medical Device Deficiencies**

Not applicable

### 8.3.10. Medication Errors

Medication errors may result from the administration or consumption of the study intervention by the wrong participant, or at the wrong time, or at the wrong dosage strength.

Exposures to the study intervention under study may occur in clinical trial settings, such as medication errors.

Safety Event	Recorded on the CRF	Reported on the CT SAE Report Form to Pfizer Safety Within 24 Hours of Awareness
Medication errors	All (regardless of whether associated with an AE)	Only if associated with an SAE

Medication errors include:

- Medication errors involving participant exposure to the study intervention;
- Potential medication errors or uses outside of what is foreseen in the protocol that do or do not involve the study participant.

Such medication errors occurring to a study participant are to be captured on the medication error page of the CRF, which is a specific version of the AE page.

In the event of a medication dosing error, the sponsor should be notified within 24 hours.

Whether or not the medication error is accompanied by an AE, as determined by the investigator, the medication error is recorded on the medication error page of the CRF and, if applicable, any associated AE(s), serious and nonserious, are recorded on the AE page of the CRF.

Medication errors should be reported to Pfizer Safety within 24 hours on a CT SAE Report Form **only when associated with an SAE**.

### 8.4. Treatment of Overdose

While overdose following topical administration is unlikely, there is a possibility that an excess of crisaborole may be applied. If too much crisaborole has been applied, the excess can be wiped off. Investigator should monitor the participant for any AEs/SAEs.

### 8.5. Pharmacokinetics

Blood samples of approximately 2 mL will be collected for measurement of plasma concentrations of crisaborole and its identified main oxidative metabolites (AN7602 and AN8323) as specified in the [SoA](#) at 1 sampling time point prior to the first dose of study intervention on Day 1 in C3291027 (around 12 hours post the last dose of C3291032).

Instructions for the collection and handling of biological samples will be provided in the laboratory manual or by the sponsor. The actual date and time (24-hour clock time) of each sample will be recorded.

The actual times may change, but the number of samples will remain the same. All efforts will be made to obtain the samples at the exact nominal time relative to dosing. Collection of samples up to and including 10 hours after dose administration that are obtained within 10% of the nominal time relative to dosing (eg, within 6 minutes of a 60-minute sample) will not be captured as a protocol deviation, as long as the exact time of the collection is noted on the source document and the CRF. Collection of samples more than 10 hours after dose administration that are obtained  $\leq 1$  hour away from the nominal time relative to dosing will not be captured as a protocol deviation, as long as the exact time of the collection is noted on the source document and the CRF. This protocol deviation window does not apply to samples to be collected more than 10 hours after dose administration at outpatient/follow-up visits with visit windows.

The skin around venous access area must be thoroughly cleansed prior to blood sample collection with mild soap and water followed by an isopropyl wipe.

The date/time of the blood collection and the date/time of the last dose of study intervention in C3291032 captured in the CRF.

Samples will be used to evaluate the PK of crisaborole and its identified main oxidative metabolites (AN7602 and AN8323). Each plasma sample will be divided into 1 aliquot for PK. Samples collected for analyses of crisaborole and its identified main oxidative metabolites (AN7602 and AN8323) plasma concentration may also be used to evaluate safety or efficacy aspects related to concerns arising during or after the study, for metabolite identification and/or evaluation of the bioanalytical method, or for other internal exploratory purposes.

Genetic analyses will not be performed on these plasma samples. Participant confidentiality will be maintained.

Samples collected for measurement of plasma concentrations of crisaborole and its identified main oxidative metabolites (AN7602 and AN8323) will be analyzed using a validated analytical method in compliance with applicable SOPs.

The PK samples must be processed and shipped as indicated in the instructions provided to the investigator site to maintain sample integrity. Any deviations from the PK sample handling procedure (eg, sample collection and processing steps, interim storage or shipping conditions), including any actions taken, must be documented and reported to the sponsor. On a case-by-case basis, the sponsor may make a determination as to whether sample integrity has been compromised.

## **8.6. Pharmacodynamics**

Pharmacodynamic parameters are not evaluated in this study.

### **8.7. Genetics**

Genetics (specified analyses) are not evaluated in this study.

### **8.8. Biomarkers**

Biomarkers are not evaluated in this study.

### **8.9. Immunogenicity Assessments**

Immunogenicity assessments are not included in this study.

### **8.10. Health Economics**

Health economics/medical resource utilization and health economics parameters are not evaluated in this study.

## **9. STATISTICAL CONSIDERATIONS**

Detailed methodology for summary and statistical analyses of the data collected in this study is outlined here and further detailed in a SAP, which will be maintained by the sponsor. The SAP may modify what is outlined in the protocol where appropriate; however, any major modifications of the primary endpoint definitions or their analyses will also be reflected in a protocol amendment.

### **9.1. Estimands and Statistical Hypotheses**

#### **9.1.1. Estimands**

The primary objective in this study is the safety evaluation. There is no pre-specified estimand for the safety evaluation and the safety endpoints will be analyzed descriptively. In addition, there is no secondary objective in this study.

### **9.2. Sample Size Determination**

Sample size will be determined by the number of participants who enroll from the qualifying parent studies. It is estimated that at least 150 participants (ie, 20 participants for under 2 years old and 130 participants for 2 years and older) are expected to join from the currently planned qualifying parent studies. Analyses performed, including interim evaluations, if any, will primarily be for safety though some measures of efficacy may be analyzed.

### **9.3. Analysis Sets**

For purposes of analysis, the following analysis sets are defined:

Participant Analysis Set	Description
Full Analysis Set	All participants who take at least one dose of study intervention.

Safety	All participants who take at least one dose of study intervention.
PK Analysis Set	All participants who take at least one dose of study intervention in Study C3291032 and who have at least one concentration value.

#### **9.4. Statistical Analyses**

The SAP will be developed and finalized before any analyses are performed and will describe the analyses and procedures for accounting for missing, unused, and spurious data. This section is a summary of the planned statistical analyses of the primary and secondary endpoints.

##### **9.4.1. General Considerations**

The efficacy objective is exploratory in this study. Efficacy analyses will be descriptive in nature; there will be no formal hypothesis testing, though 95% two-sided confidence intervals will be reported.

For the purpose of analysis of efficacy measures, the baseline values are defined as the baseline values from the participant's qualifying parent study.

##### **9.4.2. Primary Endpoint(s)**

The primary endpoint of incidence of safety events will be analyzed using descriptive measures such as percentages and exposure-adjusted incidence rates along with confidence intervals. No statistical hypotheses will be tested.

##### **9.4.3. Secondary Endpoint(s)**

There are no secondary endpoints in this study.

##### **9.4.4. Tertiary/Exploratory Endpoint(s)**

###### **9.4.4.1. Efficacy Endpoints**

The measures of efficacy (EASI and ISGA scores and other patient/observer reported outcome measures) will be summarized using descriptive statistics, such as number and percent, mean, standard deviation and quartiles at each visit where measured. Displays using stratification by participation in qualifying studies will also be included.

Exploratory analyses may also be performed.

Further details will be specified in the SAP.

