- Day 1 will be the same day as EOT visit of Study C3291032 or C3291031. Procedure done at Day 1 Visit of next treatment cycle. Depending upon ISGA score and investigator's judgment, participant will initiate an "On-treatment Cycle" or "Off-treatment Cycle".
- Obtain written informed consent (from adult participant or parent/legal guardian of pediatric participant) and assent (from pediatric participant, as applicable) before any study procedures are performed.
- Procedure done at Day 29 (concomitant treatment, physical examination, %BSA, ISGA, Regional ISGA-face, EASI, Peak Pruritus NRS/Patient Reported Itch Severity Scale/ Observer Reported Itch Severity Scale, urine pregnancy test and AE/SAE) and Screening (medical history including AD history/prior AD treatment) of Study C3291032 or procedure done at Week 24 (concomitant medications/therapies, physical examination, height/length and

Visit Identifier a Abbreviations used in this table may be found in Appendix 6 .	Enrollment Visit	Intervention Period			Follow-up Contact b	
	Visit 1	Visit 2-13		Unplanned Visit to initiate study intervention during Off-Treatment Cycle	Visit 14	Visit 15
	Day 1 c	Weeks 4, 8, 12, 16, 20, 24, 28, 32, 36, 40, 44, 48			Week 52/EOT/ET	Week 56/EOS
		Days 29, 57, 85, 113, 141, 169, 197, 225, 253, 281, 309, 337			Day 365/EOT/ET	Day 393/EOS At least 28 days after last study dose
Visit Window		Start Day of On-Treatment Cycle c	Start Day of Off-Treatment Cycle c			
		±7 days based on Day 1			±7 days based on Day 1	+7 days based on Week 52/EOT/ET

weight, %BSA, EASI, ISGA, Observer Reported Itch Severity Scale, and AE/SAE) and Screening (medical history including AD history/prior AD treatment) of Study C3291031 will serve as Enrollment Visit data for Study C3291027.

- f. For all female participants biologically capable of having children (refer to Section 10.4.2 for definition of a female of childbearing potential). The participant and his/her parent/legal guardian will be instructed regarding the contraception method requirement and informed of the requirement to conduct a urine pregnancy test. Pediatric female participant who has not experienced menarche is not required to perform pregnancy testing. If the pediatric female participant starts menarche during the study, pregnancy testing will be performed.

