3.4. Baseline Variables

For the purpose of analysis of efficacy and patient/observer reported outcomes endpoints, the baseline values are defined as the baseline values from the participant's parent phase 3 study.

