6.3. Other Endpoint(s)

6.3.1. Efficacy Endpoints

6.3.1.1. % Change from Baseline in EASI Over Time

- Analysis Set: FAS (see [Section 4](#)).
- Analysis Methodology: Descriptive statistics (see [Section 5.2](#)) and 95% two-sided confidence intervals for the mean for observed data and % change from baseline in EASI over time

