6.4. Subset Analyses

Summary statistics for % change from baseline in EASI, achievement of improvement in ISGA, achievement of success in ISGA will be presented by subgroup below.

- Age (years) group (2-11, 12-17, < 18 , ≥ 18).

Descriptive statistics and 95% confidence intervals will be presented for each defined category of each subgroup.

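### The protocol promises efficacy displays split by parent study; the SAP has none and gives no reason, so some pooled by-visit summaries may mix participants whose baselines are 20 weeks apart in age.

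*Protocol*

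**What the plan says.** Protocol 9.4.4.1 plans descriptive summaries of EASI, ISGA and the patient/observer-reported measures at each visit. It adds, without condition, "Displays using stratification by participation in qualifying studies will also be included", and then "Further details will be specified in the SAP".

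The SAP specifies each efficacy and itch endpoint on the full analysis set, with the itch scales restricted to their age bands. For EASI, for example, section 6.3.1 gives "95% two-sided confidence intervals for the mean for observed data and % change from baseline in EASI over time". None of these sections splits by parent study. Section 6.4 has age as its only factor, in the groups "Age (years) group (2-11, 12-17, < 18 , ≥ 18", and applies it only to EASI % change and the two overall ISGA endpoints ("achievement of improvement in ISGA, achievement of success in ISGA will be presented by subgroup below").

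Two clocks are in use:
- **Baseline.** SAP 3.4: "the baseline values are defined as the baseline values from the participant's parent phase 3 study".
- **Visits.** SAP Appendix 1 defines the windows from C3291027 Day 1.

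The footnotes to the Schedule of Activities (Protocol 1.3) place Day 1 on the parent study's end-of-treatment day. They take enrollment-visit data from Day 29 of C3291032 "or procedure done at Week 24" of C3291031.

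**The concern.** A pooled figure at a given extension week can average participants at two quite different times since baseline, and from two populations: infants aged 1 to under 24 months at parent entry, and participants aged 2 years or older. The display that would let a reader see this is the one that the protocol promised and the SAP omits. In a study with no hypothesis test, the by-visit tables are the whole efficacy result, so whether they can be interpreted matters even though the endpoints are exploratory.

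**Working it through.** **1. Planned numbers (Protocol 9.2).** 20 under 2 years + 130 aged 2 or older = 150, which reproduces the stated figure. Taking the two age strata as C3291031 and C3291032, the planned C3291031 share is 20/150 = 13.3%.

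**2. Time since parent baseline at entry.** C3291032: (29 − 1)/7 = 4 weeks. C3291031: 24 weeks, assuming that its Week 24 is counted from its own baseline.

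**3. Time since parent baseline at extension week w.** 4 + w for C3291032 and 24 + w for C3291031. The pooled mean is (130 × (4 + w) + 20 × (24 + w))/150.

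| Extension visit | C3291032 | C3291031 | Pooled mean, planned mix |
|---|---|---|---|
| Day 1 | 4 | 24 | 6.7 |
| Week 4 | 8 | 28 | 10.7 |
| Week 24 | 28 | 48 | 30.7 |
| Week 52 | 56 | 76 | 58.7 |

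The gap is 20 weeks throughout, and the pooled mean describes neither stratum.

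**4. Which endpoints can mix.**
- Change from baseline, both parents eligible: EASI % change, EASI50, EASI75, treatable %BSA, ISGA success, Observer Reported Itch (under 6 years).
- Not a change from baseline, but pooling different treatment histories: ISGA improvement (a score of 0 or 1).
- C3291032 only, so no mixing: Regional ISGA-face (restricted in Protocol 8.1.4); Peak Pruritus NRS (12 years and older) and Patient Reported Itch (6 to under 12), because age is fixed at consent in the prior study (Protocol 8.1.7.1).

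**5. Do the age groups stand in for the split?** A participant under 2 falls only in the under-18 group, together with C3291032 children. The 12–17 and adult groups hold no C3291031 participants. The 2–11 group holds none if age is taken at parent entry, but SAP 6.4 does not say when age is taken. If it is taken at extension Day 1, 24 weeks is 168/30.4375 = 5.5 months, so anyone older than about 24 − 5.5 = 18.5 months at C3291031 entry would be counted in 2–11. On either reading no row shows C3291031 entrants alone.

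**6. Possible size.** The shift of a pooled mean away from the C3291032 mean is the C3291031 share times the difference between strata. The documents give no such difference, so 5, 10 and 20 percentage points of EASI % change are assumed, with 130 C3291032 participants:

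| C3291031 participants | Share | Shift for 5 / 10 / 20 points |
|---|---|---|
| 0 | 0% | 0 / 0 / 0 |
| 10 | 7.1% | 0.36 / 0.71 / 1.43 |
| 20 | 13.3% | 0.67 / 1.33 / 2.67 |

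The share is larger for Observer Reported Itch, which covers only those under 6. The number of C3291032 entrants aged 2 to 5 is not given. Assuming 20 to 60 of them beside 20 from C3291031, the C3291031 share is 20/40 = 50% down to 20/80 = 25%.

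**The case against.** The strongest reply is that the study was terminated. SAP version 2 (7 January 2021) lists section 6.4 among those revised because participants were few and exposure was brief. Planned numbers and late visits may therefore never have been realised, and mixing needs C3291031 entrants. The lack of an under-2 group fits there having been none. So does the calendar: C3291031 was still only planned on 20 May 2020, and reaching its Week 24 by the SAP version 2 date means starting by about 23 July 2020 (168 days earlier). This stands as a limit on size. It does not settle the point, because the SAP gives no counts by parent study, still names both studies as sources, and does not mention the by-study displays in its change table.

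The SAP may also modify the protocol, and only major changes to the primary endpoint need an amendment. That stands too. A reader might infer a protocol breach, but the documents support only an unexplained omission, and whether SAP version 1 held the displays cannot be seen.

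Finally, pooled summaries on the parent baseline are the protocol's own design, and the stratified displays were to come in addition. SAP Appendix 1 states openly where its windows start. A reader might conclude that the pooled row should be demoted, or that stratifying would reveal the effect of a given treatment duration. Neither follows. The protocol sets no ranking of displays, and on/off cycles that depend on ISGA in a single-arm study make exposure vary within each stratum. The split would expose the mixing, not remove it from the pooled row.

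**Conclusion.** The concern holds in a limited form. The protocol's commitment is unconditional, the SAP does not deliver it, and no reason is given. If any C3291031 participants enrolled, the pooled by-visit summaries of the six change-from-baseline endpoints in step 4 combine times since baseline of about 4 + w and 24 + w weeks, and the age groups do not separate them.

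It would be tempting to say that every pooled change-from-baseline figure is affected, that 13% of participants carry an older baseline, or that Week 52 mixes 56 and 76 weeks. The first is wrong, since three endpoints come only from C3291032. The other two describe the planned study, not the terminated one.

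The conclusion assumes that at least one C3291031 participant enrolled and that C3291031 Week 24 is counted from that study's baseline. Severity is low to moderate, because the endpoints are exploratory, descriptive and untested.

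**What to change.** In SAP 6.3 and 6.4:
- Add displays by parent study, alongside the pooled ones, for EASI % change, EASI50/75, treatable %BSA, ISGA success, ISGA improvement and Observer Reported Itch. Treatable %BSA is not named in Protocol 9.4.4.1 but has the same problem.
- Report the number of participants from each parent study.
- Label visits as weeks since C3291027 Day 1, and give the nominal time since parent baseline for each stratum.

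If no C3291031 participants, or too few, enrolled before termination, give the counts and state that the displays are dropped for that reason.

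The cost is one by-variable in existing tables, or one sentence in the SAP. The downside is small C3291031 cells with wide intervals.
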